8.1.3.3. Visit 1: Post-Lung Transplant (between days 2 - 7)

The study staff will meet the subject in their HUP hospital room, three days after their lung transplant.

Initiating antiviral treatment

Treatment with the study drug will begin when the patient has a detectable and quantifiable HCV RNA post-transplantation and the donor and/or recipient have had an HCV genotype ascertained to guide treatment. As appropriate, subjects being discharged will be provided with a sufficient supply of the study drug.

As with any scientific protocol, safety will be considered before treating the patients. The treating physician will evaluate the patient's overall condition and make a judgment on whether initiating treatment is safe.

The following research procedures and activities will be performed:

- Assess for Adverse Events
- Obtain medication data
- Research Phlebotomy, including the NS5A drug resistance assay testing as appropriate (See Section 8.2.1 for complete list)
- Dispense study drugs

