5.2. Specific aims

Primary aims:

1. Primary efficacy objective: To determine sustained virologic response (SVR) rates of open-label Zepatier, Epclusa, or another appropriate antiviral treatment in hepatitis C virus (HCV) negative patients who receive a lung transplant from an HCV-infected donor, leading to post-transplantation de-novo HCV infection.
2. Primary safety objective: To determine the safety of administration of open-label Zepatier, Epclusa, or another appropriate antiviral treatment among HCV-negative patients who receive a lung transplant from an HCV-infected donor and develop post-transplant HCV infection.

Secondary aims:

1. To determine 1-year graft survival rates of HCV-negative lung transplant patients who receive a lung transplant from an HCV-infected donor, including those who spontaneously clear HCV and those who receive open-label Zepatier, Epclusa, or another appropriate antiviral treatment upon development of de-novo HCV.
2. To evaluate rates of spontaneous clearance of HCV among HCV-negative patients who receive a lung transplant from an HCV-infected donor.
3. To compare the quality-of-life of HCV-negative patients receiving a lung transplant from a HCV-infected donor to those of similar patients remaining on the waitlist for a standard deceased donor lung transplant.

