7.1.2. Administration of Zepatier

Merck & Co will manufacture, package, and label Zepatier drug. There will be one bottle per subject containing a 28-day supply (28 capsules) of 100/50 mg Zepatier tablets. Daily dose will be one tablet.

The Investigational Drug Services (IDS) pharmacy, directed by [name], will only be required to store and distribute Zepatier. Sofosbuvir and Ribavirin will be purchased and sourced locally. Both of these medications will be purchased and stored by the IDS pharmacy at Penn. Ribavirin will be generic and the manufacturer will vary depending on monthly price fluctuations.

Zepatier will be picked up from the investigational drug services (IDS) pharmacy by the research staff at 28-day intervals. The study staff will deliver the medication to the subjects at their study visits (patients expected to be at home by the time that HCV therapy is initiated and patients will be given medication at their scheduled post-transplant/study visit). Treatment with the study drug will begin within 4 weeks post-transplant. If hepatitis C is not cured after a subject has received Zepatier, he or she will be treated with a second regimen that includes Zepatier plus Sovaldi (Sofosbuvir) and Ribavirin. Any patient (male or female) receiving ribavirin as part of the first- or second-line regimen will be required to use two methods of birth control while on Ribavirin therapy, with continuing two forms of birth control for up to 6 months after the last dose of the study drug.

If patients have baseline NS5A drug resistance assay testing that demonstrates polymorphisms at positions M28, Q30, L31, and/or Y93, treatment with Zepatier will be extended to 16 weeks, rather than 12 weeks, and renally-adjusted Ribavirin at the clinician's discretion will be initiated, and continued for the remainder of therapy (until the 16 week mark). Such a strategy will provide optimal treatment, without delaying therapy prior to receipt of results of NS5A drug resistant testing.

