8.1.3.6. Visit 4 Post-Lung Transplant (day 28 ± 3 days)

Visit #4 should occur 4 weeks (28 ± 2 days) after the subject's lung transplant and coincide with the subject's regularly scheduled post-transplant follow-up visit. The staff will call the subject 1-2 days before the visit. During this phone call, the research staff will remind the subject where to go for the study visit, to take their routine and study medications as they usually would prior to the visits and if a fibroscan is needed, inform the subject and remind him/her to not eat or drink for three hours before the study visit.

The subject will arrive at the study site outpatient clinic. The following procedures and activities will be performed:

- Assess for Adverse Events
- Obtain medication data
- Research Phlebotomy (See Section 8.2.1 for complete list)
- Fibroscan (elastography of liver)
- Health Status Questionnaire (RAND-36) (to assess changes in health status from pre- to post-transplant)
- Pill count and verbal assessment for drug adherence
- Replenish study drug as appropriate with the DAA prescribed from the specialty pharmacy
- Schedule appointments for the follow-up visits

HCV Non-Transmission

It is possible that a subject may not develop chronic HCV infection, either due to non-transmission or spontaneous clearance of HCV by week 4 (defined as an initial positive HCV RNA and subsequent undetectable HCV RNA without treatment). If a subject has an undetectable HCV RNA based on the week 4 HCV RNA, a repeat HCV RNA will be checked at week 8 to ensure non-infection with HCV, rather than a false-negative HCV RNA. If the week 8 HCV RNA confirms lack of infection (undetectable week 8 HCV RNA), then no further treatment will be needed. Subjects will be assessed at a study visit and HCV RNA levels re-checked at week 16 and 28 post-lung transplantation. Should any subject spontaneously clear HCV without treatment, another subject will replace them in order to meet our planned treatment sample size.

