8.2. Study schedule of procedures

8.2.1. Visits, lab testing, and other clinical testing

See next page for table.

Transplanting HCV Lungs into HCV Negative Lung Recipients

Protocol V5.0, November 2020

Week(s) post-KT		Day(s) post-KT		Visit Schedule		Research Visit Activities					Research Labs					Standard of Care								
Week(s) post-KT	Day(s) post-KT	Visit	Study Visits	Lab-Only	Informed Consent	Assess Adverse Events	Current Medications	Fibroscan	RAND-36 Questionnaire	HBV DNA HIV AB & LFTs	HBV Core Antibody	Urine Preg Test	Urine Protein/Cre Ratio	HCV RNA	Viral Kinetics (optional)♦	NSSA Resistance**	Genotyping of donor and/or recipient	Vitals & Physical Exam	Surveillance biopsy	CMP*	CBC	Tacrolimus		
Screening					✓	✓	✓	✓	✓	✓	✓	✓	✓	✓				✓						
1 (Begin treatment)	Day 2 - 7	V1	✓			✓	✓				✓■			✓	✓	✓	✓	✓	✓	✓	✓	✓		
1	7 ± 1 day			✓			✓							✓	✓					✓	✓	✓	✓	
2	10 ± 1 day	V2	✓			✓	✓							✓	✓				✓	✓	✓	✓	✓	
2	14 ± 1 day			✓			✓							✓	✓				¥	✓	✓	✓	✓	
3	21 ± 3 day	V3	✓			✓	✓							✓	✓				✓	✓	✓	✓	✓	
4	28 ± 3 day	V4	✓			✓	✓	✓	✓					✓	✓	✓			✓	✓	✓	✓	✓	
6	42 ± 7 day	V5	✓			✓	✓				✓■			✓	✓				✓	✓	✓	✓	✓	
8	56 ± 7 day	V6	✓			✓	✓							✓	✓				✓	✓	✓	✓	✓	
10	70 ± 7 day	V7	✓			✓	✓								✓				✓	✓	✓	✓	✓	
12	84 ± 7 day	V8	✓			✓	✓				✓■			✓	✓	✓			✓	✓	✓	✓	✓	
13 (End treatment)†	91 ± 7 day			✓			✓								✓									
16 (SVR 4)†	112 ± 14 day	V9	✓†			✓	✓							✓	✓			✓†	✓	✓	✓	✓	✓	
20 (SVR 8)	140 ± 7 day			✓										✓	✓				✓	✓	✓	✓	✓	
24 (SVR 12)	168 ± 14 day	V10	✓			✓		✓	✓					✓	✓	✓			✓	✓	✓	✓	✓	
28†	196 ± 7 day			✓											✓					✓	✓	✓	✓	✓
32	224 ± 7 day			✓											✓					✓	✓	✓	✓	✓
36 (SVR 24)	252 ± 7 day			✓										✓	✓	✓			✓	✓	✓	✓	✓	
40	280 ± 14 day			✓										✓					✓	✓	✓	✓	✓	
52	365 ± 14 day	V11	✓			✓		✓	✓					✓	✓	✓			✓	✓	✓	✓	✓	

* CMP=comprehensive metabolic panel which includes basic metabolic panel and liver function tests
care blood draw

** As appropriate ♦Viral Kinetics testing can be done anytime there is a standard of

[†]If patients require the 16 weeks of therapy, the last 4 weeks would be the same as weeks 9-12 of therapy [■]Only if HBV Core Antibodies are positive.

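### The week-1 treatment start cuts short the untreated four weeks that define spontaneous clearance, so the aim 2 rate is biased downward by an amount the plan leaves open

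*Combined protocol and SAP*

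**What the plan says.** **The aim.** Secondary aim 2 in section 5.2 is: "To evaluate rates of spontaneous clearance of HCV among HCV-negative patients who receive a lung transplant from an HCV-infected donor". The synopsis lists the same rate as a secondary endpoint.

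**The definitions.** Section 8.1.3.6 separates non-transmission from "spontaneous clearance of HCV by week 4 (defined as an initial positive HCV RNA and subsequent undetectable HCV RNA without treatment". The Abstract also speaks of clearance in the first four weeks. Section 9.2.3 combines clearance and non-transmission in one outcome: undetectable RNA at weeks 1-4 with no treatment given. Both 8.1.3.6 and 9.2.3 add confirmatory HCV RNA tests at weeks 8, 16 and 28.

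**When treatment starts.** Four places bear on this.
- Section 8.1.3.3 (Visit 1, days 2-7): "Treatment with the study drug will begin when the patient has a detectable and quantifiable HCV RNA post-transplantation", provided that "the donor and/or recipient have had an HCV genotype ascertained to guide treatment". The treating physician must also "make a judgment on whether initiating treatment is safe". Dispensing the drug is on the list of Visit 1 activities.
- Section 8.2.1: the day 2-7 row carries the label "Begin treatment", and the end of treatment is placed at week 13.
- Section 7.1.2: treatment starts within 4 weeks of transplant, with "patients expected to be at home by the time that HCV therapy is initiated".
- Section 6.2.1: eligibility for treatment is any detectable HCV RNA by week 4, with no requirement that it be quantifiable.

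No passage holds treatment back until week 4.

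**The concern.** To count as a clearer in the strict sense, a recipient must first be viremic and then become undetectable while untreated. Under 8.1.3.3, quantifiable viremia is also the event that starts treatment once a genotype is in hand and the physician agrees. Entry to the risk set and the end of observation are then caused by the same event, and the clearance rate partly measures how soon the centre treats.

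Two things are at stake. A low or zero count could be read as evidence about the natural course of donor-derived infection, and section 4.1 says the pilot is meant to lead to a larger randomized trial. The clearances that are seen would also tend to come from a selected group: recipients whose RNA was detectable but not quantifiable, or whose treatment was delayed for genotyping or safety. Ending observation at first dose is therefore not independent of the chance of clearing.

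**Working it through.** The plan states no clearance rate, non-transmission rate or precision target, so there is no figure of its own to reproduce.

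**Step 1. Which start does the schedule assume?** Section 8.2.1 puts the end of treatment at day 91. A 12-week course is 84 days, and 91 - 84 = day 7. SVR 12 is at day 168; subtracting 84 days of follow-up and 84 of treatment gives day 0. Both point to week 1. Section 8.1.3.4 has a pill count at day 10, and 6.3.2 places recipient genotyping, when there is no donor result, in the first week. The upper limit of 4 weeks in 7.1.2 does not fit these rows, and neither does its expectation that patients are at home, since Visit 1 takes place in the hospital room.

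**Step 2. How much clearance can be seen?** Let c be the true probability of clearing over 28 untreated days among viremic recipients, and w the untreated days after first viremia. Assume a constant hazard:

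observable clearance p = 1 - (1 - c)^(w/28)

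For c = 10% and w = 7: 1 - 0.90^0.25 = 2.6%. The values of c are assumptions.

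| True c | w = 0 | w = 7 | w = 14 | w = 21 | w = 28 |
|---|---|---|---|---|---|
| 5% | 0% | 1.3% | 2.5% | 3.8% | 5% |
| 10% | 0% | 2.6% | 5.1% | 7.6% | 10% |
| 30% | 0% | 8.5% | 16.3% | 23.5% | 30% |

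The share retained is about 25-28% at 7 days, 51-54% at 14 days and 76-78% at 21 days. These are upper values, because a clearance counts only if a blood draw catches it before the first dose. A hazard that rises over the window would make the loss larger; one that falls would make it smaller.

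**Step 3. What would a zero mean?** The chance of at least one observed clearance among 11 viremic subjects is 1 - (1 - p)^11. For c = 10% it is 1 - 0.90^11 = 69% with 28 untreated days, and 1 - 0.90^(11 × 7/28) = 25% with 7. So none would be seen 75% of the time instead of 31%, through timing alone.

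**Step 4. The 9.2.3 composite.** With t the never-viremic share (assumed), the composite rate is t + (1 - t)p. For t = 10% and c = 10%:
- 28 days: 0.10 + 0.90 × 0.10 = 19.0%
- 7 days: 0.10 + 0.90 × 0.026 = 12.3%, of which 10 points are non-transmission
- 0 days: 10%, all of it non-transmission

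The composite moves towards t as the untreated time shrinks. How far non-transmission dominates depends on t, which the documents do not give.

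**The case against.** A reader might infer that the window is removed altogether, that the observed rate falls to about zero, and that aim 2 cannot be addressed. The documents do not support that.
- Treatment is not automatic at the first positive. Section 8.1.3.3 needs quantifiable RNA, a genotype and a safety judgment. A recipient with detectable but unquantifiable RNA stays untreated and is drawn again through day 28, so an untreated positive-then-negative sequence can occur.
- The start date is not settled. Section 7.1.2 permits up to 4 weeks, and under the same model 14 or 21 untreated days would keep about half or three quarters of the true rate.
- The outcome as defined in 9.2.3 counts never-viremic recipients. It is zero only if every recipient becomes viremic and none is seen to clear.

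These points stand. They limit the claim to a downward bias of unknown size; they do not remove it. A permitted later start is an upper limit, not a hold, and a composite made up largely of non-transmission does not give the clearance rate that aim 2 names.

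A reader might also infer that would-be clearers, treated and counted as cures, distort the primary SVR rate. Take the lower end of the 94-100% range in section 4.3 and assume that every would-be clearer reaches SVR. A 10% share of such subjects adds 0.10 × (1 - 0.94) = 0.6 points, and 30% adds 1.8 points. One subject in 11 is 9.1 points, so this is not a material threat.

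Finally, the endpoint is descriptive and small. Even with a full 28 days, 0/11 has an exact upper limit of 1 - 0.025^(1/11) = 28.5%. That is fair, but imprecision does not excuse a bias in a known direction. Non-transmission remains assessable, helped by the tests at weeks 8, 16 and 28.

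**Conclusion.** The treatment-start passages conflict with the untreated window used to define clearance, and with one another. If 8.1.3.3 and 8.2.1 are followed, the strict 8.1.3.6 clearance rate understates true four-week clearance. The direction is clear from the text; the size depends on untreated days that the plan does not fix. Under the constant-hazard illustration about a quarter of the true rate is visible at 7 days, half at 14 and three quarters at 21. The hazard shape and the true rates are assumptions.

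The effect is confined to one descriptive secondary endpoint and the primary SVR analysis stands. The plan should be changed, because as written a low clearance count could not be separated from early treatment.

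**What to change.** 1. In aim 2 (section 5.2), the synopsis endpoint, 9.2 and 9.2.3, replace the single rate with two results.
   - **Non-transmission:** the proportion of all transplanted subjects with no detectable HCV RNA at any draw before antiviral treatment, confirmed at weeks 8, 16 and 28.
   - **Clearance:** the number cleared among viremic subjects, with observation ending at the first antiviral dose. List each subject's untreated days from first positive to first dose, and state that subjects treated at first viremia give no information on clearance.
2. Record the dates of first positive RNA and first dose. The documents do not show the CRF, so check that both are captured.
3. Reconcile the start-of-treatment statements in 6.2.1, 7.1.2, 8.1.3.3 and 8.2.1, including detectable against quantifiable RNA. This review takes no view on when treatment should start.

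The cost is some rewording and two dates per subject. The clearance claim becomes narrower, and with about 11 subjects it stays imprecise.

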8.1.3.3.1. Management of patients with genotype 1 HCV and NS5A resistance variants

Patients with Genotype 1a and Genotype 1 with an unknown subtype will have baseline NS5A drug resistance assay testing. This will be checked at start of treatment. If patients have polymorphisms at positions M28, Q30, L31, and/or Y93, treatment with Zepatier will be extended to 16 weeks, rather than 12 weeks, and renally-adjusted Ribavirin at the clinician's discretion will be initiated, and continued for the remainder of therapy (until the 16 week mark). Such a strategy will provide optimal treatment, without delaying therapy prior to receipt of results of NS5A drug resistant testing. Under such a scenario, all of the study procedures referenced above and below will be extended by 4 weeks. Any patient (male or female) receiving ribavirin as part of the first- or

second-line regimen will be required to use two methods of birth control while on Ribavirin therapy, with continuing two forms of birth control for up to 6 months after the last dose of the study drug.

8.1.3.3.2. Management of patients with positive HBV Core Antibody

For patients with a positive HBV Core Antibody, HBV-DNA levels will be checked every 6 weeks while on Zepatier (or Epclusa or another appropriate antiviral treatment) and LFTs will be closely monitored. HBV therapy may be considered the transplant team as medically appropriate.

8.1.3.4. Visit 2: Post-Lung Transplant (day 10 ± 1 day)

Visit #2 should occur two weeks (10 ± 2 days) after the subject's lung transplant and coincide with the subject's regularly scheduled post-transplant follow-up visit. The staff will call the subject 1-2 days before the visit. During this phone call, the research staff will remind the subject where to go for the study visit, to take their routine and study medications as they usually would prior to the visits and if a fibroscan is needed, inform the subject and remind him/her to not eat or drink for three hours before the study visit.

The subject will arrive at the study site outpatient clinic. The following procedures and activities will be performed:

- Assess for Adverse Events
- Obtain medication data
- Research Phlebotomy (See Section 8.2.1 for complete list)
- Pill count and verbal assessment for drug adherence
- Schedule appointments for follow-up visits

8.1.3.5. Visit 3: Post-Lung Transplant (day 21 ± 3 days)

Visit #3 should occur three weeks (21 ± 3 days) after the patient's lung transplant and coincide with the subject's regularly scheduled post-transplant follow-up visit. The staff will call the subject 1-2 days before the visit. During this phone call, the research staff will remind the subject where to go for the study visit, to take their routine and study medications as they usually would prior to the visits and if a fibroscan is needed, inform the subject and remind him/her to not eat or drink for three hours before the study visit.

The subject will arrive at the study site outpatient clinic. The following procedures and activities will be performed:

- Assess for Adverse Events
- Obtain medication data
- Research Phlebotomy (See Section 8.2.1 for complete list)
- Pill count and verbal assessment for drug adherence
- Schedule appointments for follow-up visits

8.1.3.6. Visit 4 Post-Lung Transplant (day 28 ± 3 days)

Visit #4 should occur 4 weeks (28 ± 2 days) after the subject's lung transplant and coincide with the subject's regularly scheduled post-transplant follow-up visit. The staff will call the subject 1-2 days before the visit. During this phone call, the research staff will remind the subject where to go for the study visit, to take their routine and study medications as they usually would prior to the visits and if a fibroscan is needed, inform the subject and remind him/her to not eat or drink for three hours before the study visit.

The subject will arrive at the study site outpatient clinic. The following procedures and activities will be performed:

- Assess for Adverse Events
- Obtain medication data
- Research Phlebotomy (See Section 8.2.1 for complete list)
- Fibroscan (elastography of liver)
- Health Status Questionnaire (RAND-36) (to assess changes in health status from pre- to post-transplant)
- Pill count and verbal assessment for drug adherence
- Replenish study drug as appropriate with the DAA prescribed from the specialty pharmacy
- Schedule appointments for the follow-up visits

HCV Non-Transmission

It is possible that a subject may not develop chronic HCV infection, either due to non-transmission or spontaneous clearance of HCV by week 4 (defined as an initial positive HCV RNA and subsequent undetectable HCV RNA without treatment). If a subject has an undetectable HCV RNA based on the week 4 HCV RNA, a repeat HCV RNA will be checked at week 8 to ensure non-infection with HCV, rather than a false-negative HCV RNA. If the week 8 HCV RNA confirms lack of infection (undetectable week 8 HCV RNA), then no further treatment will be needed. Subjects will be assessed at a study visit and HCV RNA levels re-checked at week 16 and 28 post-lung transplantation. Should any subject spontaneously clear HCV without treatment, another subject will replace them in order to meet our planned treatment sample size.

8.1.3.7. Visits 5-7: Post-Lung Transplant (day 42±7, day 56±7, day 70±7)

Visit #5 should occur 6 weeks (42±7 days) after the subject's lung transplant and will coincide with the subject's regularly scheduled post-transplant follow-up visit. Visit #6 should occur 8 weeks (56±7 days) after the subject's lung transplant and will immediately follow the subject's regularly scheduled post-transplant follow-up visit. Visit #7 should occur 10 weeks (70±7 days) after the subject's lung transplant and will immediately follow the subject's regularly scheduled post-transplant follow-up visit.

For both visits, the staff will call the subject 1-2 days before the visit to remind subject of visit. During this phone call, the research staff will remind the subject where to go for the study visit, to take their routine and study medications as they usually would prior to the visits and, if a fibroscan is needed, inform the subject and remind him/her to not eat or drink for three hours before the study visit.

The following procedures and activities will be performed:

- Assess for Adverse Events
- Obtain medication data
- Research Phlebotomy (See Section 8.2.1 for complete list)
- Replenish study drug
- Pill count and verbal assessment for drug adherence
- Schedule appointments for follow-up visits

The staff will replenish the subject's 28-day supply of the Zepatier study drug or Epclusa or another appropriate antiviral therapy sometime during visits #5 & 6, depending on when the subject began treatment.

